### **2.7.2.5 Time to event analysis for reinfection**

Reinfection is defined as appearance of asexual parasites after clearance of initial infection with a genotype different from those parasites present at baseline. Reinfection must be confirmed by PCR analysis.

Incidence rates of reinfection at Day 29 will be estimated by the Kaplan-Meier method based on the subset of FAS patients who have clearance of initial infection before Day 15.

Time to event (reinfection) will be calculated from the time of first study medication to the date of first event if a patient experiences the event and will be censored at the time of last parasite assessment if a patient does not experience the event. Patients who experienced recrudescence will be censored at the first time of recrudescence.

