5.5.6 Rescue medication

The following circumstances warrant discontinuation of study treatment and the implementation of rescue medication (see [Section 6.5.8](#)):

Early treatment failure (ETF)

ETF is defined within this protocol as:

1. Clinical decline or lack of improvement (per Investigator) at 24 hours after first dose of treatment.
2. Development of any clinical complications (described in the WHO definition of complicated/severe malaria (WHO Guidelines 2010)) in the presence of parasitaemia within 72 hours of the first dose of treatment
3. Parasitaemia $> 75\ 000/\mu\text{L}$ at or after 12 hours post-dose
4. Parasitaemia \geq baseline with or without fever at 36 hours after first dose of treatment
5. Any parasitaemia based on microscopy with fever, 48 hours post-dose
6. Parasitaemia $> 100/\mu\text{L}$ based on microscopy with or without fever, 72 hours post-dose

Late Clinical Failure (LCF)

Development of danger signs or severe malaria on any day between Study Day 5 and Day 29 in the presence of parasitaemia without previously meeting any of the criteria of ETF.

Presence of parasitaemia and axillary temperature $\geq 37.5^\circ\text{C}$ on any day between Study Day 5 and Day 29 without previously meeting any of the criteria of ETF.

Late Parasitological Failure (LPF)

Presence of parasitaemia on any day between Study Day 5 and Day 29 and axillary temperature $< 37.5^\circ\text{C}$ without previously meeting any of the criteria of ETF or LCF.

Commencement of rescue medication with Coartem may occur after start of trial medications and up to Study Day 28 as deemed necessary by the investigator. Any patient on KAE609 who

did not need rescue medication up to Study Day 28, will be given Coartem at end of the study at Study Day 29. Rescue medication according to local guidance will be used for severe malaria.

Patients randomized to Coartem and meeting treatment failure definition will be further treated by rescue medication as per local treatment guidance.

The patients receiving rescue medication will not be replaced and will not discontinue the study (i.e., all the examinations as per the assessment schedule and all CRF pages for this patient will need to be completed).

Safety blood tests (Full Blood Count (FBC) and blood chemistry) will be collected on the initial day of rescue medication dosing. Blood films and blood sampling for parasite count and genotyping must be taken before giving the rescue treatment.

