9.5.1.4 Recrudescence

Reinfection is defined as appearance of asexual parasites after clearance of initial infection with a genotype different from those parasites present at baseline.

Recrudescence is defined as appearance of asexual parasites after clearance of initial infection with a genotype identical to that of parasites present at baseline. Recrudescence must be confirmed by PCR analysis.

Incidence rates of recrudescence at Study Day 29 will be estimated by Kaplan-Meier method based on the subset of FAS patients who have clearance of initial infection by Study Day 7. Time to recrudescence will be calculated from the time of first study medication to the date of first event if a patient experience the event and be censored at the time of last parasite assessment if a patient does not experience the event.

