#### 2.1.1 General definitions

**Study treatment:** KAE609 is the investigation treatment whereas Coartem® will serve as control. They are referred to as study treatments in the document.

Summary results will be presented by cohort and treatment group. Besides, a pooled Coartem group from all cohorts will be presented from all tables as applicable. The following abbreviated treatment group labels will be used as the column headers in the CSR outputs:

- KAE609 10 mg SD

- KAE609 10 mg QD 3 days
- KAE609 25 mg SD
- KAE609 25 mg QD 3 days
- KAE609 50 mg SD
- KAE609 50 mg QD 3 days
- KAE609 75 mg SD
- KAE609 150 mg SD
- KAE609 225 mg SD or KAE609 110 mg SD
- Coartem
- Pooled Coartem

**Baseline:** The last measurement made prior to and including administration of the first dose of study treatment. Note this may include measurements taken on the day of randomization (e.g. lab, ECG, vital signs). If a patient did not receive any dose of study treatment then the randomization date will be used as the date of first dose of study treatment.

**Study day:** Study day will be calculated with respect to the first dose of study treatment. The first day of administration of study treatment (first dose) is defined as Day 1. Day -1 will be the day before Day 1. Day 0 does not exist. If a patient did not receive any dose of study treatment then the randomization date will be used as the date of first dose of study treatment.

For assessments collected on or after Day 1, study day = date of assessment – date of first dose of study treatment + 1.

For assessments collected prior to Day 1, study day = date of assessment - date of first dose of study treatment.

At the end of trial, full statistical analyses will be performed by cohort and treatment group. Coartem data from all cohorts will also be pooled.

Tail of KM plots: Since the tail of KM plots after the day of last planned assessment is not reliable due to small numbers of patients at risk, the time to event will be truncated to the planned last day (Day 29) regardless of censoring.

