### **2.7.2.4 Recrudescence**

Recrudescence is defined as appearance of asexual parasites after clearance of initial infection with a genotype identical to that of parasites present at baseline. Recrudescence must be confirmed by PCR analysis.

Incidence rates of recrudescence at Study Day 29 will be estimated by Kaplan-Meier method based on the subset of FAS patients who have clearance of initial infection before Day 15. Time to recrudescence will be calculated from the time of first study medication to the date of first event if a patient experiences the event and be censored at the time of last parasite

assessment if a patient does not experience the event. Patients who experienced a new infection will be censored at the first time of new infection.

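### The Day 29 incidence of recrudescence and of reinfection is a Kaplan-Meier complement with the other event censored: a net risk that overstates the proportion of patients affected, mainly for reinfection

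*SAP*

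**What the plan says.** For recrudescence, SAP 2.7.2.4 states: "Incidence rates of recrudescence at Study Day 29 will be estimated by Kaplan-Meier method". It adds: "Patients who experienced a new infection will be censored at the first time of new infection". For reinfection, SAP 2.7.2.5 states: "Incidence rates of reinfection at Day 29 will be estimated by the Kaplan-Meier method". It adds the mirror rule: "Patients who experienced recrudescence will be censored at the first time of recrudescence". Both analyses use the FAS patients whose initial infection cleared before Day 15. SAP 2.1.1 fixes the horizon for the Kaplan-Meier plots: "the time to event will be truncated to the planned last day (Day 29) regardless of censoring". Neither section names a net-risk estimand, an independence assumption or a competing-risk estimator.

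Protocol 9.5.1.4 also uses Kaplan-Meier for recrudescence, but its only stated censoring is that time to recrudescence is to "be censored at the time of last parasite assessment if a patient does not experience the event". It gives no time-to-event rule for reinfection. SAP Section 4, which is the place for changes to protocol-specified analyses, says NA.

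Protocol 5.5.6 makes a recurrence of either kind a late failure. Late parasitological failure, for example, is "Presence of parasitaemia on any day between Study Day 5 and Day 29 and axillary temperature" below 37.5°C. Late failure is a circumstance for rescue medication. Follow-up does not stop there: "The patients receiving rescue medication will not be replaced and will not discontinue the study".

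**The concern.** Each analysis takes the patient out of the risk set at the first recurrence of the other type. The Kaplan-Meier complement then treats that patient as someone who could still have had the event of interest, and shares the patient's weight among those still at risk. This answers how often reinfection would occur if recrudescence did not exist. It does not answer how many patients were reinfected by Day 29, which is the plain meaning of an incidence at Day 29.

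Incidence of recrudescence at Day 29 is the only endpoint listed for its own secondary objective (Protocol Table 2-1, SAP Table 1-2). Reinfection is in the list of secondary efficacy variables (Protocol 9.5.1, SAP 2.7.1). A reader of the report would take both figures as proportions of patients. They are not, and together they can exceed the proportion with any recurrence.

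**Working it through.** The documents state no expected incidence for either event, so there is no planned figure to reproduce. The check compares the SAP's estimator with the cumulative incidence over a range of rates.

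**Inputs**
- Visits at Days 8, 11, 15, 22 and 29 (SAP Table 5-6). No other dropout is assumed, so cumulative incidence equals the simple proportion.
- Recrudescence 36%: Protocol 3.6 reports 4 (36%) in the MIC study. 4/11 = 36.4%, but the 11 is inferred; Protocol 9.8 lists 25 patients in a study at 10 to 30 mg.
- Reinfection 9%: Protocol 3.6 reports one new infection in the 75 mg PoC extension study. 1/11 = 9.1% if the 11 patients of Protocol 1.1 are the denominator.
- These two rates come from different studies and serve only as an illustration. All other rates, and all timing, are assumptions.

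**Formulas**, with a(t) events of interest, b(t) competing events and N(t) at risk at visit t:
- SAP estimate: 1 − Π[1 − a(t)/N(t)], where N falls by a + b after each visit.
- Cumulative incidence: Σ a(t)/N(0).

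**Closed form, proportional hazards.** With cumulative incidences 0.36 and 0.09, the Kaplan-Meier complement is 1 − (1 − 0.45)^(c/0.45).
- Reinfection: 1 − 0.55^0.2 = 11.3%, against 9.0%.
- Recrudescence: 1 − 0.55^0.8 = 38.0%, against 36.0%.

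**Discrete visits.** Same timing: both events spread in proportion to the interval lengths 7, 3, 4, 7 and 7 days. Early/late: recrudescence shares 0.15/0.30/0.30/0.20/0.05 and reinfection shares 0/0.05/0.15/0.35/0.45 over the five visits. Cells give the SAP estimate in percent, with the excess in points.

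| Cumulative incidence, recrudescence / reinfection | Timing | Reinfection | Recrudescence |
|---|---|---|---|
| 5 / 10 | same | 10.2 (+0.2) | 5.2 (+0.2) |
| 5 / 10 | early/late | 10.4 (+0.4) | 5.0 (+0.0) |
| 36.4 / 9.1 | same | 10.8 (+1.7) | 38.0 (+1.6) |
| 36.4 / 9.1 | early/late | 12.8 (+3.7) | 36.7 (+0.4) |
| 36.4 / 20 | same | 24.1 (+4.1) | 40.3 (+3.9) |
| 36.4 / 20 | early/late | 28.5 (+8.5) | 37.3 (+0.9) |
| 60 / 10 | same | 14.0 (+4.0) | 63.5 (+3.5) |
| 60 / 10 | early/late | 20.0 (+10.0) | 60.9 (+0.9) |
| 60 / 20 | early/late | 41.2 (+21.2) | 62.1 (+2.1) |

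The SAP estimate was never below the cumulative incidence. The two agree if every recurrence falls at Day 29. In the last row the two SAP figures add to 41.2 + 62.1 = 103.3%, while 80% of patients had any recurrence.

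**Hand examples**
- n = 20. Recrudescence in 2, 3 and 2 patients at Days 11, 15 and 22; one reinfection at Day 22 and one at Day 29. At risk: 15 at Day 22, then 15 − 2 − 1 = 12 at Day 29. Reinfection: 1 − (14/15)(11/12) = 14.4%, against 2/20 = 10%. Recrudescence: 7/20 = 35% by both methods.
- n = 10. Six recrudescences by Day 22 and one reinfection at Day 29. Reinfection: 1/4 = 25%, against 1/10 = 10%.

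**In patients.** At 36.4%/9.1% and n = 20 the excess for reinfection is 0.017 × 20 = 0.3 to 0.037 × 20 = 0.7 of a patient.

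**The case against.** Kaplan-Meier with the other event censored is a legitimate net-risk estimate under independence, and two net risks need not add to the any-recurrence proportion. The same censoring of new infections appears in the Kaplan-Meier analysis of PCR-corrected ACPR (Protocol 9.5.1.1, SAP 2.7.2.1.1), where malaria methodology is cited. This stands as a reason to leave that analysis alone and to keep the present curves. It does not justify an incidence label in two sections that state neither the estimand nor the assumption.

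A reader might infer that cross-censoring creates a false dose pattern in reinfection, because the excess grows with recrudescence. The documents do not support that. Suppose two arms share a net reinfection risk of 20%, with independent net recrudescence of 0% and 50% and proportional hazards. The Kaplan-Meier complement is 20% in both. Cumulative incidence is 20% in the first and, in the second, [0.223/(0.223 + 0.693)] × (1 − 0.8 × 0.5) = 14.6%. The net risk is flat; the cumulative incidence falls, because fewer patients remain to be reinfected.

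A reader might also infer that the first recurrence ends observation. It does not: under Protocol 5.5.6 rescued patients are examined on schedule to Day 29. What ends is time at risk in the SAP's analysis and, once rescue is given, time on the assigned drug alone.

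SAP Table 2-4 marks a binary summary for both variables, which may show the crude proportion. No text defines it, so it cannot be relied on. It is also true that no decision rests on these figures: secondary comparisons with Coartem are ruled out (SAP 2.7), and the regimen decision in SAP 2.5.2 rests on safety results.

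**Conclusion.** The point holds as one of estimand and labelling. What the SAP calls the Day 29 incidence is a net risk, valid as such only under an unstated independence assumption, and it exceeds the proportion of patients who had the event whenever competing recurrences come earlier. The excess falls mainly on reinfection in arms with much recrudescence: about 2 to 4 points at the illustrative 36%/9%, more at higher assumed rates, and negligible where recrudescence is rare. Recrudescence moves by about 2 points or less when it comes first; if both events share a time course, the absolute excess is similar for the two.

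These sizes depend on borrowed rates with inferred denominators and on assumed timing. In arms of 10 to 20 the effect is often one patient or less, and the analyses are secondary and descriptive. Separately, for recrudescence the SAP adds a censoring rule that Protocol 9.5.1.4 does not state, and Section 4 does not record it. The protocol has no such rule for reinfection to depart from. This is worth correcting, but it does not threaten the trial's main conclusions.

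**What to change.** - In SAP 2.7.2.4 and 2.7.2.5, report the Aalen-Johansen cumulative incidence of each event at Day 29, with the other as competing event, side by side by arm. The other censoring rules can stay.
- Keep the present cross-censored Kaplan-Meier curves as a supportive analysis, labelled net risk and with the independence assumption stated. An arm comparison of reinfection should show both, since cumulative incidence also depends on recrudescence.
- Leave the Kaplan-Meier ACPR analyses unchanged.
- Record in SAP Section 4 the departure from Protocol 9.5.1.4. Date the entry, because the SAP was already updated once after database lock.

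The cost is a few lines of text and the EVENTCODE option in PROC LIFETEST, which SAP 5.5.3 already uses. No new data are needed. The downside is that the main figure is less directly comparable with Kaplan-Meier recrudescence estimates from elsewhere, and the retained curve covers that.

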### **Handling of missing values/censoring/discontinuations**

The patient will be censored at the time of last parasite assessment if a patient does not experience the event. Undertermined treatment failures due to missing PCR data will be considered as censored at the time of treatment failure.

## **2.8 Safety Analysis**

All safety parameters will be analyzed by cohort and treatment group based on the safety.

### **2.8.1 Adverse events (AEs)**

The number and percentage of patients with treatment emergent adverse events will be presented. The treatment emergent adverse events (events started on or after the first dose of study medication or events present prior to the first dose of study medication but increased in severity based on preferred term) will be summarized by MedDRA primary System Organ Class (SOC) and Preferred Term (PT).

Adverse events will be summarized by presenting, for each cohort and treatment group, the number and percentage of patients having at least one AE, having an AE in each primary system organ class and having each individual AE (preferred term). Summaries will also be presented for AEs by severity (CTC Toxicity grade) and for study treatment related AEs. If a patient reported more than one adverse event with the same preferred term, the adverse event with the greatest severity will be presented. If a patient reported more than one adverse event within the same primary system organ class, the patient will be counted only once with the greatest severity at the system organ class level, where applicable.

The MedDRA version used for reporting the adverse events will be described in a footnote.

The most common adverse events reported ( $\geq z$  % in any group for each preferred term in the table by SOC and PT) will be presented in the clinical study report by descending frequency according to its incidence in overall group starting from the most common event. Here the threshold value  $z$  is set to 5 (%) but it may be updated following review of the dry run outputs.

Separate summaries will be provided for death, serious adverse events, severe malaria, other significant adverse events leading to treatment discontinuation and adverse events leading to dose adjustment.

Patients who experienced a grade 3 or grade 4 AE will be summarized.

For the legal requirements of ClinicalTrials.gov and EudraCT, two required tables on treatment emergent adverse events which are not serious adverse events with an incidence greater than 5% and on treatment emergent serious adverse events and SAE suspected to be related to study treatment will be provided by system organ class and preferred term on the safety set.

If for a same patient, several consecutive AEs (irrespective of study treatment causality, seriousness and severity) occurred with the same SOC and PT:

- a single occurrence will be counted if there is  $\leq 1$  day gap between the end date of the preceding AE and the start date of the consecutive AE
- more than one occurrence will be counted if there is  $> 1$  day gap between the end date of the preceding AE and the start date of the consecutive AE

For occurrence, the presence of at least one SAE / SAE suspected to be related to study treatment / non SAE has to be checked in a block e.g., among AE's in a  $\leq 1$  day gap block, if at least one SAE is occurring, then one occurrence is calculated for that SAE.

Number of deaths resulting from SAEs suspected to be related to study treatment and number of deaths resulting from SAEs irrespective of causality will be provided.

The adverse events will be summarized for the following subgroup.

- Sex (male vs female)

Algorithms for date imputations is provided in Appendix 5.

### **2.8.1.1 Adverse events of special interest / grouping of AEs**

The adverse events of special interest are defined in the Case retrieval Sheet (CRS) which is updated for each MedDRA dictionary. The CRS data are stored in RDCRS SAS dataset corresponding to a subset of eCRS SAS view for which the following filtering criteria are applied

-Drug code = KAE609

-the latest version of MedDRA at the time of final database lock.

-End date is null (this means this is the latest CRS version)). Potential risks based on the current CRS are listed in [Table 2-1](#).

The number and percentage of patients with these special AEs will be summarized. In addition, listings of related adverse events will be provided.

Newly occurring liver enzyme abnormalities and QTcF (QT interval corrected for heart rate according to Fredericia) abnormalities will be summarized. Only QTcF and HR will be summarized for the intext table. QTcF will be summarized in post-text tables and will be presented in the listing. (see [Sections 2.8.2 and 2.8.3.1](#)).

**Table 2-1 List of safety topics of interest**

Safety Topic Of Interest	SOC	MedDRA Code	MedDRA Term	MedDRA Level	MedDRA Qualifier
QTc prolongation	Investigations	20000001	Torsade de pointes/QT prolongation	SMQ	Broad
Adrenal gland disorder	Endocrine disorders	10001353	Adrenal gland disorders	HLGT	
	Investigations	10001339	Adrenal cortex tests	HLT	
	Metabolism and nutrition disorders	10014412	Electrolyte and fluid balance conditions	HLGT	
	Vascular disorders	10011954	Decreased and nonspecific blood pressure disorders and shock	HLGT	
	Investigations	10001373	Adrenal medulla tests	HLT	
Hepatotoxicity	Hepatobiliary disorders	20000006	Drug related hepatic disorders-comprehensive search	SMQ	Broad
Phototoxicity	Skin and subcutaneous tissue disorders	10072982	Photosensitivity and photodermatitis conditions	HLT	
	Skin and subcutaneous tissue disorders	10052566	Rashes, eruptions and exanthems NEC	HLT	
	Skin and subcutaneous tissue disorders	10054786	Skin burning sensation	PT	
	Skin and subcutaneous tissue disorders	10037087	Pruritus	PT	
	Skin and subcutaneous tissue disorders	10015151	Erythemas	HLT	
Anemia	Blood and lymphatic system disorders	20000029	Haematopoietic erythropenia	SMQ	Broad
	Blood and lymphatic system disorders	10002055	Anaemias haemolytic NEC	HLT	
	Blood and lymphatic system disorders	10002052	Anaemias haemolytic immune	HLT	

Gastrointestinal disorders (e.g., nausea, vomiting, diarrhea)	Gastrointestinal disorders	20000140	Gastrointestinal nonspecific symptoms and therapeutic procedures	SMQ	Broad
Semen discoloration (yellow)	Reproductive system and breast disorders	10013358	Spermatogenesis and semen disorders	HLT	
	Investigations	10016462	Fertility analyses	HLT	
Hypoglycemia	Metabolism and nutrition disorders	90000029	Hypoglycemia (Standard)	NMQ	Narrow
Development of clinical resistance to KAE609 in P. vivax and P. falciparum	Infections and infestations	10035499	Plasmodia infections	HLT	
	Investigations	10033903	Parasite identification and serology	HLT	
	General disorders and administration site conditions	90000022	Lack of efficacy (PSUR) [Standard]	NMQ	Broad

## 2.8.2 Laboratory data

Descriptive statistics will be generated for all clinical laboratory tests performed (actual values and changes from baseline) for three groups of laboratory tests (hematology, clinical chemistry and urinalysis) by laboratory test, cohort, and treatment group. Change from baseline will only be summarized for patients with both baseline and post baseline values and will be calculated as:

$$\text{change from baseline} = \text{post baseline value} - \text{baseline value}$$

The following laboratory parameters will be analyzed for hematology test group: hemoglobin, platelets, white blood cell count, Reticulocytes, hematocrit, red blood cell (RBC) count, lymphocytes, lymphocytes (%), monocytes, monocytes (%), eosinophils eosinophils (%), neutrophils, neutrophils(%), basophils, and basophils (%).

The following laboratory parameters will be analyzed for clinical chemistry test group creatinine, total bilirubin (TBL), direct bilirubin, alanine aminotransferase (ALT), aspartate aminotransferase (AST), alkaline phosphatase (ALP), glucose, blood urea nitrogen (BUN), sodium, potassium, calcium, uric acid, gamma glutamyltransferase (GGT), magnesium, phosphate, chloride, haptoglobin, total protein, albumin, INR and LDH.

For liver enzymes (ALT, AST, etc.), the shift table of CTCAE grades relative to baseline will be provided. Summary with frequency and percentage of patients with liver related events as defined in [Table 2-2](#) will be provided by cohort and treatment:

